8.4 Reporting Procedures – Notifying the IRB

8.4.1 Adverse Event Reporting

Unexpected, related, and harmful adverse events will be reported to the IRB within 10 working days of discovery. Subjects will be followed until the resolution of the adverse event.

8.4.2 Serious Adverse Event Reporting

In addition to determining the appropriate intervention and ensuring the subject is medically treated, all serious adverse events will be reported to the IRB within 24 hours of discovery.

8.4.3 Unanticipated Problem Reporting

Incidents or events that meet the OHRP criteria for UPs require the creation and completion of an UP report form. It is the principal investigator's responsibility to report UPs to the IRB. The UP report will include the following information:

- Protocol identifying information: protocol title and number, PI's name, and the IRB project number;
- A detailed description of the event, incident, experience, or outcome;
- An explanation of the basis for determining that the event, incident, experience, or outcome represents an UP;
- A description of any changes to the protocol or other corrective actions that have been taken or are proposed in response to the UP.

To satisfy the requirement for prompt reporting, UPs will be reported using the following timeline:

- UPs that are SAEs will be reported to the IRB within 24 hours of the investigator becoming aware of the event.
- Any other UP will be reported to the IRB within 10 working days of the investigator becoming aware of the problem.
- All UPs should be reported to appropriate institutional officials (as required by an institution's written reporting procedures), the supporting agency head (or designee), and OHRP promptly, within 2 weeks of the IR's receipt of the report of the problem from the investigator.

8.5 Study Halting Rules

Administration of the study agent will be halted when three grade 3 AEs determined to be "probably related" are reported to the PI. The PI will notify the IRB immediately when the third grade 3 event is reported and enrollment screens will stop accepting new study participants and the active participants will be contacted via phone and if necessary certified mail, to immediately discontinue the spray.

8.6 Safety Oversight

It is the responsibility of the Principal Investigator to oversee the safety of the study at his/her site. This safety monitoring will include careful assessment and appropriate reporting of adverse events as noted above, as well as the construction and implementation of a site data and safety-monitoring plan. Medical monitoring will include a regular assessment of the number and type of serious adverse events.

An independent licensed physician who is a specialist in neurology or otolaryngology will be appointed to monitor subject safety. [name] of the Department of Neurology will perform this role; [name] is a disinterested third party and is well acquainted with good research practices. In addition to individual subject monitoring at each visit, the PI will systematically review accumulated data, adverse events, and other relevant events in the study: (1) assess the timeliness, completeness, and quality of the data collected, (2) assess the adherence to protocol requirements, especially measures taken to protect participant safety, and (3) assess the benefit/risk ratio of study procedures monthly.

A summary of AEs and outcomes of these monthly reviews will be submitted to the IRB every 6 months. The PI and [name] will meet and review data after every 15 subjects have been enrolled, and will be provided with the following data prior to this meeting: (1) all adverse events reported, and (2) subject recruitment, enrollment, and dropout numbers. During the meeting, they will review these data and have 30 days to generate a report, which reflects their opinion of whether the study should be permitted to continue and whether any changes need to be made. This report will then be submitted to the IRB. If any serious adverse events occur during the study, Drs. [name] and [name] will be apprised of them within 24 hours of the event and will be provided unblinded information with regard to the participants' treatment assignment and corresponding study visit. They will then provide suggestions for the progress of the study, as well as determine whether modifications to the protocol are needed. Any additional events of pulmonary edema will be reported to the IRB as Reportable New Information, as per NYU SOM IRB policy.

Patients will be screened for depression and suicidality at the screening visit and during the weekly follow-up visits via direct questioning and in the THI (questions 5 and 21). Any patient with worsening depression or suicidal ideation will be immediately referred to their psychologist/psychiatrist or the psychiatric emergency department. The PI will personally call the appropriate person (clinician, ED, or emergency services) as deemed appropriate for the individual subject. Although there have been reports in the literature linking low plasma and CSF oxytocin levels with suicide, oxytocin nasal spray has been demonstrated to have antidepressant and anxiolytic effects, and as such, we do not expect treatment to worsen depression, but rather improve mood.

9 Statistical Considerations

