- 3. A 6 week double-blinded phase in which half of the participants will receive oxytocin nasal spray and half will receive placebo nasal spray. Neither the PI nor subject will know which drug they are receiving. However, the study coordinator will have access to this information as required to assign the medications.

Patients will come to the Preston Robert Tisch Center for Men's Health for study visits every 2 weeks and be administered the VAS and THI/CGI scales by the research coordinator or principal investigator. The screening visit will be the most comprehensive and include obtaining informed consent, a physical exam with vital signs, laboratory studies, questionnaires, an ECG, and review of medical and medication history to confirm all inclusion criteria are met and that there are no exclusion criteria present. During these visits they will have urine testing for sodium and osmolality. Every other week, they will receive a phone call from study staff to discuss their experience using the study drug and monitor for any adverse effects. They will complete the Tinnitus Functional Index questionnaire over the phone as well. When the subjects come in for their study visit, 4 weeks after the baseline period, they will receive enough study medication for the rest of the study, to allow for randomization to placebo or active drug at that time.

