7.1 Study Procedures/Evaluations

Patients will come to the Preston Robert Tisch Center for Men's Health for study visits every 2 weeks and be administered the VAS and THI/CGI scales by the research coordinator or principal investigator. The screening visit will be the most comprehensive and include obtaining informed consent, a physical exam with vital signs, laboratory studies, questionnaires, an ECG, and review of medical and medication history

to confirm all inclusion criteria are met and that there are no exclusion criteria present. During these visits they will have urine testing for sodium and osmolality. Every other week, they will receive a phone call from study staff to discuss their experience using the study drug and monitor for any adverse effects. They will complete the Tinnitus Functional Index questionnaire over the phone as well. When the subjects come in for their study visit, 4 weeks after the baseline period, they will receive enough study medication for the rest of the study, to allow for randomization to placebo or active drug at that time.

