8.2.3 Expectedness

The PI will be responsible for determining whether an AE is expected or unexpected. An AE will be considered unexpected if the nature, severity, or frequency of the event is not consistent with the risk information previously described for the study agent.

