9.6.1.3 Breaking the Study Blind/Participant Code

The blind shall not be broken until the final data analysis, however:

All adverse events (AEs) occurring during the course of the clinical drug trial will be brought to the attention of the PI. For significant AEs and serious adverse events (SAEs), the PI will decide on an appropriate intervention. Most AEs should not normally lead to the breaking of the treatment assignment code. However, if the AE is so severe that it significantly compromises the well-being of the subject, the PI may decide to break the blindness code and withdraw the subject from the study.

In the case of AEs of intermediate severity, as when a certain laboratory parameter or clinical sign or symptom gradually deviates from normality, the PI will treat these deviations using standard and well accepted treatment guidelines and continue to follow the patient until said abnormalities resolve. If standard treatments fail to resolve the abnormalities, the PI may decide to break the blind.

10 Source Documents and Access to Source Data/Documents

Source data is all information, original records of clinical findings, observations, or other activities in a clinical trial necessary for the reconstruction and evaluation of the trial. Source data are contained in source documents. Examples of these original documents, and data records include: hospital records, clinical and office charts, laboratory notes, memoranda, subjects' diaries or evaluation checklists, pharmacy dispensing records, recorded data from automated instruments, copies or transcriptions certified after verification as being accurate and complete, microfiches, photographic negatives, microfilm or magnetic media, x-rays, subject files, and records kept at the pharmacy, at the laboratories, and at medico-technical departments involved in the clinical trial. It is acceptable to use CRFs as source documents. If this is the case, it should be stated in this section what data will be collected on CRFs and what data will be collected from other sources.

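### For SAEs in the blinded phase, section 8.6 discloses the arm automatically, on its natural reading to the PI, while sections 4.1 and 9.6.1.3 keep the PI blind unless the PI decides otherwise

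*Combined protocol and SAP*

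**What the plan says.** Section 8.6 (Safety Oversight) appoints an independent physician to monitor safety. It says that this physician and the PI "will meet and review data after every 15 subjects have been enrolled" and report jointly on whether the study should continue. If any SAE occurs, two doctors are to be told of it within 24 hours and "will be provided unblinded information with regard to the participants' treatment assignment and corresponding study visit". The same two then advise on the study's progress and on protocol changes. The section sets no test of need beyond the event being serious.

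Section 9.6.1.3 opens with "The blind shall not be broken until the final data analysis, however" and then lists exceptions. The PI decides on the intervention for SAEs. The PI may break the code if an event significantly compromises the participant's well-being, or if standard treatment of a lesser abnormality fails. It adds: "Most AEs should not normally lead to the breaking of the treatment assignment code".

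Section 4.1 says of the blinded phase: "Neither the PI nor subject will know which drug they are receiving".

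On the PI's other tasks, section 8.2.3 states: "The PI will be responsible for determining whether an AE is expected or unexpected". Under section 7.1, participants will "be administered the VAS and THI/CGI scales by the research coordinator or principal investigator".

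**The concern.** One section makes disclosure of the arm a standing consequence of an SAE. Another makes it a decision to be taken on the facts of the case. Site staff facing a blinded-phase SAE cannot follow both.

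The person affected also matters. The PI decides whether an event is expected and may be the clinician who assesses relatedness. Someone who knows that an event occurred on placebo is less likely to call it drug-related, and someone who knows it occurred on oxytocin is more likely to. Nothing in the plan requires these judgements to be recorded before the arm is disclosed.

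Sections 9.4.3 and 9.4.4 summarize AEs by drug-relatedness and by phase and/or arm. In a pilot meant to yield initial safety estimates, a few labels set with knowledge of the arm could shift that comparison. Sections 8.5 and 9.4.7.1 halt dosing after three grade 3 events judged probably related, so one label is a third of the threshold.

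**Working it through.** The plan states no figure on this point. The check sets the sections side by side, followed by two illustrations of scale.

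**1. Who receives the code.** The names in section 8.6 are removed. The sentences just before describe one pair, the PI and the independent physician, who meet and report together. The sentence just after gives the two doctors that same advisory function. No other pair appears in the section. That the PI is one of the two is therefore an inference, though a strong one.

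**2. Which events.** All participants receive active drug in the 9-week non-blinded phase, so an SAE there has nothing to unblind. The conflict is confined to the 6-week blinded phase.

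**3. Nature of the conflict.** Section 8.6 makes disclosure automatic for any SAE. Section 9.6.1.3 makes it discretionary, with a condition attached. The SAE definition in section 8.1.2 includes important medical events that are not immediately life-threatening, so some SAEs will trigger section 8.6 without meeting the condition in section 9.6.1.3.

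**4. Timing.** The 24 hours in section 8.6 applies to being told of the event. The unblinded information follows in the same sentence without its own deadline.

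**5. Which judgements are exposed.** Expectedness belongs to the PI (8.2.3). Relatedness belongs to the assessing clinician (8.2.2, 8.3), who may or may not be the PI. The halting rule uses the category probably related, whereas section 8.2.2 defines only related and not related. An effect on that count is therefore possible but cannot be traced exactly.

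**6. Outcome rating.** Section 2.4.1.1 says participants with an SAE are withdrawn at once, while sections 5.7.1.1 and 9.6.1.3 word withdrawal as something that may happen. If withdrawal follows, the remaining contact is the early termination visit (7.2.5). It is held only if the participant agrees and covers VAS, THI and CGI. A rating made there could be carried forward under the LOCF rule in section 9.4.

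**7. How often it might arise.** Assume 30 randomized and an SAE risk p per participant in the blinded phase; the documents give no p. The expected number is 30p, and the chance of at least one is 1 − (1 − p)^30.

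| Assumed p | Expected SAEs | Chance of at least one |
|---|---|---|
| 0.01 | 0.3 | 0.260 |
| 0.02 | 0.6 | 0.455 |
| 0.05 | 1.5 | 0.785 |
| 0.10 | 3.0 | 0.958 |

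**8. What one code says about others.** Section 9.6.1.1 specifies block randomization without a block size. In a 1:1 block of size b, once one assignment is known, another member is in the opposite arm with probability (b/2)/(b − 1).

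| Assumed b | Probability of opposite arm | Other members of the block, of 30 |
|---|---|---|
| 2 | 1/1 = 1.00 | 1 (3%) |
| 4 | 2/3 = 0.67 | 3 (10%) |
| 6 | 3/5 = 0.60 | 5 (17%) |

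These values apply only if the PI knows the block size and who shares the block.

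**The case against.** The strongest reply is that little harm follows, and much of it stands.

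- **IRB reporting.** A reader might infer that knowing the arm could distort what reaches the IRB, since section 8.4.1 turns on unexpected and related events. The documents do not support that for SAEs. Section 8.4.2 sends every SAE to the IRB within 24 hours, and section 8.2.2 says relatedness does not decide what is reported. The label of unanticipated problem does rest on expectedness and relatedness (8.1.3), but an SAE reaches the IRB within 24 hours with or without it.
- **Expectedness.** It is judged against risk information already described for the study agent (8.2.3), which leaves less room for the arm to matter than relatedness does. This narrows the concern without removing it.
- **Outcome ratings.** A reader might infer that the VAS endpoint is compromised by an unblinded rater. If the withdrawal statement in section 2.4.1.1 governs, the unblinded participant is hardly rated again. Tinnitus loudness is also kept in the participant's own daily log, and the participant stays blind.
- **Other members of the block.** The PI would need a block structure the plan does not state. Section 9.6.1.1 keeps the log in a separate binder used by the non-blinded fellow. Participants are randomized one at a time, so others in the block may have finished or not yet started.
- **PI unblinding is not forbidden.** Section 9.6.1.3 expressly allows it for severe events. The conflict is mandatory against discretionary, not permitted against prohibited.

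What remains is the contradiction itself, and the lack of any rule that causality judgements come before disclosure.

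**Conclusion.** The concern holds for SAEs in the 6-week blinded phase. Section 8.6 requires disclosure that section 9.6.1.3 makes discretionary and that the blinding statement in section 4.1 does not foresee. This rests on reading the PI as one of the two doctors; if the sponsor meant someone else, naming the roles settles it.

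The main consequence is possible bias in expectedness and, where the PI is the assessor, in relatedness. It would show in the AE summaries by drug-relatedness and, for grade 3 events, possibly in the halting count. Bias in outcome ratings is secondary, limited mainly to the early termination visit and to conditional inference about other members of the block.

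The size cannot be fixed from the documents. The illustrations assume 30 randomized, although replacement under section 5.7.2 could raise that number, and they use assumed SAE risks and block sizes. The number of events affected is likely to be small. A change is still worth making because each label weighs heavily at this sample size and the remedy is only wording.

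**What to change.** 1. In section 8.6, name the recipients by role. Have the non-blinded fellow send the assignment for a blinded-phase SAE to the independent physician only.
2. Require severity, relatedness and expectedness to be recorded before any code break.
3. Let the PI be unblinded only through section 9.6.1.3, with date and reason logged. That route stays open as written.
4. Have any later scale rating of an unblinded participant done by someone without access to assignments. As section 4.1 stands, that rules out the study coordinator, who has such access.
5. Reconcile sections 4.1, 8.6 and 9.6.1.3 on the blind, and sections 2.4.1.1, 5.7.1.1 and 9.6.1.3 on withdrawal after an SAE.

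Steps 1 to 3 and 5 are protocol wording and use people already appointed. Step 4 may need another blinded rater for an occasional visit. The downside is small: after an SAE the PI advises on the study's progress without the code unless section 9.6.1.3 is invoked, while the independent physician has it.

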9.1 Plans (SAP)

The primary analysis is to provide an estimate of the partial eta squared effect size difference between placebo and treatment during the blinded phase of the study as well as to provide initial safety and tolerability estimates during the initial open label study phase. The effect size will be calculated and interpreted using η^2 =0.2 as a small effect, η^2 =0.5 as a medium effect, and η^2 =0.8 as a large effect (20).

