2.2 Name and Description of the Investigational Agent

The investigational product is an oxytocin nasal spray composed of: oxytocin/MG/mannitol trituration, magnesium chloride crystals, citric acid anhydrous gran., sodium citrate powder, sterile water for irrigation, and Pcca Mucolox liquid base.

The placebo nasal spray consists of magnesium chloride crystals, citric acid anhydrous gran., sodium citrate powder, sterile water for irrigation, and Pcca Mucolox liquid base. Both placebo and active drug will be handled and stored the same way, in amber glass bottles and kept between 36°F to 46°F (2°C - 8°C).

We believe this study meets the criteria for IND Exemption for the following reasons:

Oxytocin has been tested and is approved by the FDA in different indications. This will be a proof of concept study only, and therefore it is not intended to be reported to the FDA in support of a new indication. If this pilot study, proof of concept study, is successful, we plan to initiate a large-scale study that would then be used to support a new indication, requiring IND application.

We do not intend to use the results of this study to support any change in the advertising of this product and are not affiliated with any sponsors that carry vested interest in the commercial presentations of oxytocin.

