2.2.1.2 Dose Rationale (if applicable)

Although the route of administration (nasal spray) used in this study differs from the currently parenteral administration, nasal spray applications of oxytocin have been previously employed for a number of different medical and psychiatric conditions as well as in healthy controls for more than a decade. A recent meta-analysis detailed these studies in which doses of oxytocin ranged from 15 to more than 7000 IU were given without significant adverse events (20). Additionally, recommendations for the standardization of oxytocin nasal administration and guidelines for its reporting were published in the past decade (25). The authors stated "Transmucosal nasal delivery provides a non-invasive alternative route for drugs with poor systemic bioavailability after oral administration. Intranasal administration causes minimal discomfort for the patient, is simple to use, and typically results in high compliance."

Although this study will use a dosage of oxytocin that is higher than used in a previous study of tinnitus (45 IU QID vs 8 IU BID), it is well within the dose range reported in other studies in the psychiatric literature. In those studies, adverse events were rare, non-life threatening and fully reversible.

Additionally, oxytocin nasal spray has been reported in other studies to be very safe (17).

We therefore believe that neither the route of administration nor dose employed in this study would significantly increase the risks (or decrease the acceptability of the risks) associated with the use of the drug product.

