9.2 Statistical Hypotheses

We hypothesize that treatment with high dose oxytocin nasal spray will result in a large effect size as measured by partial eta squared for the difference in mean area under the curve in baseline adjusted VAS when compared to placebo during the blinded study phase.

The primary outcome measurement will be the collective area under the VAS curve above the week 3 baseline as assessed from week 3 to week 6 of the blinded study phase. The area under the curve will be determined using the linear trapezoidal method for each participant after subtracting the baseline (week 3) VAS value from each subsequent measure to determine the collective improvement/decline of the VAS measurement during the blinded study phase. The mean and standard deviation of the total area will be

calculated for each study arm (active drug and placebo) and partial eta squared effect size for the difference determined. This effect size estimate can then be used to power future comparative studies.

The same area under the curve above the baseline VAS metric will be determined separately for the nonblinded/open label study phase. The inherent bias of non-blinding may influence this metric although the relatively larger sample size (n=30) could also improve precision. Therefore, the area will be presented as a descriptive summary using the mean and standard deviation with an effect size estimate.

Secondary endpoints will consist of safety and tolerability metrics including adverse event incidence and severity, regimen adherence and voluntary study drop-out rates reported during the non-blinded and blinded study phases. The frequency and percentage of each secondary measure will be determined for the non-blinded study phase and by study arm for blinded study phase. Additionally, any changes in THI greater than 1 grade will be determined from week 3 to week 6 of the blinded study phase. The frequency and percentage of these changes will be summarized by study arm.

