9.4 Description of Statistical Methods

Data from this pilot study will be summarized separately for the non-blinded study phase and by study arm for the blinded study phases. The area under the VAS curve after subtracting baseline value will be determined using the linear trapezoidal method. These areas will be determined for the efficacy population using the last observation carried forward (LOCF). The mean and standard deviation for the non-blinded phase will be determined and the effect size for the mean area from zero calculated. For the blinded phase week 3 (after a 2 week "washout") will serve as the baseline and the area under the VAS curve from baseline will be calculated using LOCF imputation for missing post baseline data. To avoid potential cross-over effects from the 9 week non-blinded phase when all subjects receive active drug, after randomization, subjects will receive either active drug or placebo. The first 2 weeks of this 6 week period will be a washout period from statistical analysis. While subjects will still receive study drug, data collection for that phase will not begin until week 3 of that 6 week period. The mean and standard deviation in area under the VAS curve from baseline for each study arm will be determined and the partial eta effect size for the mean difference between study arms calculated. This summary will be performed for the per protocol study population as well to investigate the relative influence of missing data on the effect size determination.

Frequencies and percentages for the secondary safety and tolerability endpoints will be determined using the ITT patient population for the non-blinded study phase and all randomized participants during the nonblinded study phase. The other secondary endpoint, incidence of the change in THI of 1 point or greater, will be summarized by study arm for those participants providing at least 1 post-week 3 baseline THI measurement.

The analyses will be refined and adjusted in anticipation of study termination and data lock.

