9.4.2 Analysis of the Primary Efficacy Endpoint(s)

The primary efficacy endpoint is the area under the VAS curve from baseline for all randomized participants during the blinded study phase. The week 3 data after two week washout will serve as the baseline and the interval/ratio scaled area determined using the linear trapezoidal method. The expectation is that placebo participants' post-baseline VAS data will remain relatively consistent with baseline values while active treatment will trend post-baseline. Using an LOCF imputation strategy is therefore a conservative strategy for handling missing data by understating trending in the active treatment group without introducing trending in the placebo group. The mean and standard deviation by study arm in the area under the VAS curve from baseline will be presented along with the partial eta squared effect size estimate for the mean difference between study arms. The availability of data will be determined by study arm at each post-baseline study time point during the blinded study phase to investigate the potential influence of missing data. A per-protocol analysis will also be presented to further investigate the influence of missing data on the primary efficacy endpoint.

The area under the VAS curve from baseline will similarly be determined and analyzed separately for the open label/non-blinded study phase. Since this measure is biased by participant knowledge of treatment the effect size of the mean VAS area from baseline will be determined and cautiously interpreted.

As included in Section 9.1, the effect size will be calculated and interpreted using η^2 =0.2 as a small effect, η^2 =0.5 as a medium effect, and η^2 =0.8 as a large effect (20). These cut-offs will be used to judge the strength of the treatment relative to placebo control with medium ($\eta^2 \ge 0.5$) considered a treatment "success."

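### The success bar of partial eta squared 0.5, labelled medium, equals a standardised difference of about 2, so the pilot would almost never be called a success for a true difference of 1 or less

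*Combined protocol and SAP*

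**What the plan says.** Section 9.1 names the statistic: "The primary analysis is to provide an estimate of the partial eta squared effect size difference between placebo and treatment during the blinded phase". It then gives the reading scale: "The effect size will be calculated and interpreted using η^2 =0.2 as a small effect", followed by "η^2 =0.5 as a medium effect, and η^2 =0.8 as a large effect (20", where 20 is the reference number. Section 9.4.2 repeats the three values and gives them a decision role: "These cut-offs will be used to judge the strength of the treatment relative to placebo control with medium", meaning an eta squared of at least 0.5, counted as treatment success. Section 9.2 states the hypothesis on the same scale: "We hypothesize that treatment with high dose oxytocin nasal spray will result in a large effect size as measured by partial eta squared".

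Three other places bear on this:

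- Section 2.2 says "If this pilot study, proof of concept study, is successful, we plan to initiate a large-scale study". It does not define the word.
- Section 9.4 drops the square once: "the partial eta effect size for the mean difference between study arms calculated".
- Reference 20, the source given for the cut-offs, is cited in Section 2.2.1.2 as a meta-analysis of intranasal oxytocin studies and is listed that way in Section 17. Reference 30 in that list is a handbook on design and analysis.

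**The concern.** Eta squared is the share of total variance explained by study arm. A value of 0.5 means that treatment assignment accounts for half of all variation in VAS area between participants. That is an extreme effect to call medium, and 0.8, the effect hypothesised in Section 9.2, is more extreme still. The three values look like benchmarks for a standardised mean difference attached to the wrong statistic. That origin is an inference, since no section states it.

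The rule in Section 9.4.2 is the only criterion that the plan itself labels a success. If Section 2.2 uses the word in that sense, a pilot of a useful drug would be declared unsuccessful and the larger study would lose its stated trigger. Published labels would also mislead: with 15 per arm, an observed d of 0.9 would be reported as less than small. The more than 50% VAS improvement criterion in Section 4.1 conflicts with this rule, but that is a separate issue.

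**Working it through.** **Inputs.** Total n = 30 (Section 9.5). Half of the participants go to each arm (Section 4.1), with block randomisation (Section 9.6). The comparison is of mean area between two arms with no covariates named (Sections 9.2 and 9.4.2), so partial eta squared equals eta squared. Assumptions: 15 analysed per arm, and normally distributed area with equal variances. The plan gives no SD, alpha, power or target difference, so there is no stated power figure to reproduce, and true d is shown over a range.

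**Step 1: what the cut-offs mean.** With equal arms η² = d²/(d²+4), hence d = 2√(η²/(1−η²)).

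- 0.2: 2√(0.2/0.8) = 1.00
- 0.5: 2√(0.5/0.5) = 2.00
- 0.8: 2√(0.8/0.2) = 4.00

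In the other direction, d = 0.2, 0.5 and 0.8 give η² = 0.04/4.04 = 0.010, 0.25/4.25 = 0.059 and 0.64/4.64 = 0.138.

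**Step 2: the bar in a sample of 15 per arm.** η² = t²/(t²+28), so η² = 0.5 needs t = √28 = 5.29 (two-sided p = 0.0000125). The sample d is 5.29 × √(2/15) = 1.93. Imbalance changes little: 1.94 for 14 vs 16 and 1.97 for 12 vs 18.

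**Step 3: chance of meeting η² ≥ 0.5.** Noncentral t, 28 df, noncentrality d√7.5:

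| True d | Chance of success |
|---|---|
| 0 | 0.001% |
| 0.5 | 0.07% |
| 0.8 | 0.6% |
| 1.0 | 2.0% |
| 1.5 | 18% |
| 2.0 | 58% |

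Simulation with 300,000 trials per scenario gave 0.066%, 0.57% and 1.94% at d = 0.5, 0.8 and 1.0. At d = 0.8, 66% of trials fall below even the small cut-off of 0.2. With other arm sizes, the chance of success at d = 0.8 is 1.4% (12 vs 12) or 0.4% (10 vs 20).

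**Step 4: the unsquared reading.** If the single mention of partial eta in Section 9.4 were taken literally, the cut-offs would equal d = 0.41, 1.15 and 2.67, and success at d = 0.8 would occur in 22% of trials. The labels do not fit on that reading either.

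**Step 5: behaviour of the alternative bar.** Hedges' g = d × (1 − 3/(4×28 − 1)) = 0.973d. The condition g ≥ 0.5 in the favourable direction needs t ≥ (0.5/0.973) × √7.5 = 1.41. It is met by 8.5% of trials at d = 0, 49% at d = 0.5 and 78% at d = 0.8. A favourable η² ≥ 0.06 is met by 9.6% at d = 0. An observed g of 0.5 has a 95% CI of about −0.2 to 1.2 (noncentral-t inversion).

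**The case against.** The strongest reply is that this is a pilot whose stated product is an estimate. Sections 9.1, 9.2 and 9.5 all say so, and nothing in data collection, randomisation, analysis sets or the statistic itself is wrong. That stands: eta squared converts to d, arm means and SDs are reported, and a later trial could still be sized correctly. It does not rescue the rule in Section 9.4.2, which is prespecified and decides what the pilot is called.

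Second, the link to the go/no-go decision is an inference. Section 2.2 argues for an IND exemption and does not refer to Section 9. This also stands, so the consequence is conditional, although no other section defines success.

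Third, a strict bar may have been intended, and the documents cannot show that 0.2/0.5/0.8 on g is the right replacement. The second half is fair, and any new bar needs its own reason. On the first half, the plan gives no reason for a bar of d = 2 and calls it medium.

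Fourth, reference 20 cannot be seen here and might contain benchmarks. The citation should therefore be checked rather than presumed wrong. The missing square in Section 9.4 is one slip against consistent use elsewhere, and the finding does not depend on it.

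Finally, Section 9.4 allows the analyses to be refined before data lock. That permits the correction, but a threshold changed late and without a recorded reason would look driven by results.

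**Conclusion.** The concern holds. By algebra, the cut-offs in Sections 9.1 and 9.4.2 equal d = 1, 2 and 4. The medium bar for success is a difference of about two standard deviations (1.93 in a sample of 15 per arm), and the large effect hypothesised in Section 9.2 is about four. For any true d up to 1.0, the chance of a success verdict is at most 2.0%. The conversion assumes two equal arms without covariates. The probabilities also assume 15 analysed per arm and normal areas with equal variances, and the true d values are illustrative because the plan gives none. The damage is confined to the labels and to a go/no-go call that uses them. A lesser gap is that the rule has no direction condition, although the reported arm means would show the direction.

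**What to change.** Amend Sections 9.1, 9.2 and 9.4.2 by a dated change before data lock:

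- Report the signed active-minus-placebo difference in mean area and Hedges' g, each with a 95% CI, and apply 0.2/0.5/0.8 to g. Alternatively keep partial eta squared and restate the cut-offs as about 0.01/0.06/0.14.
- Use one name for the statistic throughout, including Section 9.4, and check the citation given for the cut-offs.
- Require the direction of lower VAS for success.
- If the bar becomes g ≥ 0.5, give a reason for it, since no section states a clinically relevant difference in area. Print its error rates from Step 5. State that it is read together with the CI, signals whether a further trial is worthwhile, and is not proof of efficacy. Dropping the word success would also resolve the point.
- State separately which effect size and scale apply to the open-label mean area from zero in Section 9.4, because the two-arm conversion does not hold there.

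The cost is SAP wording only, with no new data or participants. The price is a much easier bar: about 9% of trials with no effect would meet it, against less than 0.01% now.
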